3.2.2 SECONDARY

OBJECTIVES	ENDPOINTS	JUSTIFICATION FOR ENDPOINTS
Secondary		

OBJECTIVES	ENDPOINTS	JUSTIFICATION FOR ENDPOINTS

 • To compare, between the same two groups over the same time period, 
 1) The rate of self-reported new episodes of respiratory illness (URI or ILI), DIA and UFI. 2) The rate of self-reported new episodes of 
 a) ILI b) URI c) DIA d) UFI 3) The rate of clinically-confirmed episodes of the study syndromes 4) The rate of laboratory-confirmed episodes of the study syndromes • First event, per protocol analysis (receipt of all 3 doses) and extended per protocol analysis (receipt of at least one dose) of primary endpoint and secondary endpoints 1-7 (primary analyses will focus on all events and intention-to-treat analyses). • Sub-group analyses for potential effect measure modification of Primary Endpoint and Secondary Endpoints 1-7 by 
 1) Sex (males or females) 2) Season (spring = January cohorts; summer = May cohorts; winter = September cohorts) 	
 1. Number of self-reported new episodes of respiratory illness (URI or ILI), DIA and UFI. 2. Number of self-reported new episodes of URI 3. Number of self-reported new episodes of ILI 4. Number of self-reported new episode of DIA 5. Number of self-reported new episodes of UFI 6. Number of clinically-confirmed episodes of the study syndromes, defined as an episode resulting in a visit to the RUSVM Student Health Services with a recorded ICD10 of J00 (acute nasopharyngitis); J11 (influenza due to unidentified influenza virus); R19.7 (diarrhea) or R50.9 (fever, unspecified). 7. Number of laboratory-confirmed episodes of the study syndromes, defined as clinically-confirmed episodes with laboratory diagnosis of influenza virus, respiratory syncytial virus or metapneumovirus (URI/ILI episodes) or rotavirus or norovirus (DIA episodes) . 	
For Secondary Endpoint 1, in any week a single participant could report one of the following:
 
 • No CID episode • One CID episode (URI or ILI or DIA or UFI) • Two CID episodes (either URI or ILI, and DIA) 
By this definition, a participant cannot experience more than two CID episodes within a week, as occurrence of URI together with ILI is considered an episode of ILI only, and occurrence of URI, ILI and/or DIA precludes the occurrence of UFI.
 
We also will attempt to determine impact on etiologically confirmed outcomes but we expect few episodes to meet this criteria and thus study power will be low. Etiological confirmation will be done for a limited range of pathogens only (influenza virus, respiratory syncytial virus, metapneumovirus, rotavirus and norovirus) through an independent research protocol (RUSVM IRB protocol #17-11-FL) and the test results sent back to the RUSVM Student Health Services.

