3.2.4 SAFETY

OBJECTIVES	ENDPOINTS	JUSTIFICATION FOR ENDPOINTS
Safety		

 • To compare, between the same two groups, 
 1) The rate of solicited adverse events (AEs) through 3 days after each injection (dose 1, 2 and 3) 2) The rate of unsolicited adverse events and serious adverse events (SAEs) through four weeks after first injection • As a secondary objective, sub-group analysis for potential effect measure modification of safety endpoints by sex (males or females) 	
 1. Number of solicited self-reported events over three days following each injection of the following adverse events: 
 a. Local reactions (limited to the site of the injection): pain, erythema, oedema, pruritus and induration. b. Systemic reactions: fever, shivering, malaise, asthenia, faintness, dizziness, headache, myalgia, arthralgia, nausea and abdominal pain. c. Hypersensitivity or allergic reactions: anaphylaxis, urticaria, rash and erythema multiforme. 2. Number of unsolicited adverse events and SAEs reported to RUSVM Student Health Services through four weeks after first injection 	
Solicited adverse events are those adverse events listed in the package insert of the study intervention (Rabivax-S rabies vaccine)

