8 SAMPLE SIZE

The estimated number of participants needed to achieve the study's primary objective is 430 (215 in each group). The sample size was calculated using the approach for comparing two negative binomial rates based on true rates (Approach 2 in [17]), implemented using the function *power.nb.test* in package 'MKmisc' in R, and assuming the following parameter values:

- Alpha level = 0.05
- Targeted power = 0.8
- Event rate for control group = 2 (expected mean number of new CID episodes [composite primary endpoint] over 26 weeks)
- Rate ratio under alternative hypothesis = 0.75
- Average length of participation (accounting for drop-out and non-response) = 21 weeks (0.8 of 26-week observation period)
- Negative binomial dispersion parameter (k in [17]) = 0.4

The three nuisance parameters (average length of participation, event rate for control group and negative binomial dispersion parameter) were estimated from data collected over 7 weeks of a pilot study of rates of CID episodes in 90 RUSVM students (40 in 1st semester and 50 in 5th semester) from 21 May to 8 July, 2018 (weeks 3 through 9 of summer semester).

An internal pilot study will be done using data from the first 300 participants to complete the study. As the expected enrollment rate is <100 participants per semester, this will allow capture of seasonal variation in event rates (≥ 3 semesters in internal pilot study). The three nuisance parameters will be re-estimated from the internal pilot study data and the sample size recalculated, using a blinded sample size re-estimation method for count data [18, 19], which maintains required power without an increase in the type I error. The sample size will only be increased and not decreased on the basis of the internal pilot study (that is, if the recalculated sample size is smaller than the original sample size, the original sample size will still be used).

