14 STATISTICAL METHODS

The analysis of the primary endpoint and secondary endpoints 1-7 will be conducted after all randomized participants have completed the study (one week after receipt of the final weekly survey) or have withdrawn from the study, whichever occurs first. Primary analysis will be based on intention-to-treat analysis of all events (that is, not just occurrence of first events). The comparison of incidence rates of CID episodes (primary endpoint and secondary endpoints 1-7) between the treatment arms will be performed using a negative binomial regression model, which accounts for different lengths of observation period. Participants' number of CID episodes will be modelled as a function of treatment group, with the number of weeks of observation included as an offset in the model. This analytic model estimates the rate ratio, λ_t / λ_c , which quantifies the risk of CID episodes associated with rabies vaccination (λ_t) in comparison to placebo injection (λ_c). Statistical significance will be controlled at the 2-sided, 0.05 alpha level, and the estimated rate ratio compared with 1, assuming the following statistical hypothesis:

H_0 (null hypothesis): Rate ratio = 1

H_1 (alternative hypothesis) Rate ratio $\neq 1$

Treatment effect will be based on the coefficient in the model. Statistical significance at the pre-specified alpha level will be based on a Wald testing procedure. CID rates (primary

endpoint and secondary endpoints 1-7) for rabies vaccine and placebo, and the rate ratio, will be presented and will include 95% confidence intervals.

A detailed description of the statistical methods that will be used for the primary and secondary endpoints will be provided in a Statistical Analysis Plan (SAP).

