15 HARMS

15.1 DEFINITIONS OF ADVERSE EVENTS AND SERIOUS ADVERSE EVENTS

Definitions of adverse events (AEs) and serious adverse events (SAEs) are taken from the Office of Human Research Protections Guidance on Reviewing and Reporting Unanticipated Problems Involving Risks to Subjects or Others and Adverse Events.

Adverse event means any untoward or unfavorable medical occurrence in a participant, including any abnormal sign (for example, abnormal physical exam or laboratory finding), symptom, or disease, temporally associated with the subject's participation in the research, whether or not considered related to the subject's participation in the research.

A serious adverse event is any adverse event temporally associated with the subject's participation in research that meets any of the following criteria:

1. results in death;
2. is life-threatening (places the subject at immediate risk of death from the event as it occurred);
3. requires inpatient hospitalization or prolongation of existing hospitalization;

4. results in a persistent or significant disability/incapacity;
5. results in a congenital anomaly/birth defect; or
6. any other adverse event that, based upon appropriate medical judgment, may jeopardize the subject's health and may require medical or surgical intervention to prevent one of the other outcomes listed in this definition (examples of such events include allergic bronchospasm requiring intensive treatment in the emergency room or at home, blood dyscrasias or convulsions that do not result in inpatient hospitalization, or the development of drug dependency or drug abuse).

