15.2 CLASSIFICATION OF ADVERSE EVENTS

All adverse events (AEs) will have their relationship to study intervention assessed by the Manager of the RUSVM Student Health Services (study nurse practitioner), in consultation with the study Medical Advisor, based on temporal relationship and clinical judgment.

The following guidelines will be used to describe severity:

- **Mild** – Events require minimal or no treatment and do not interfere with the participant's daily activities.
- **Moderate** – Events result in a low level of inconvenience or concern with the therapeutic measures. Moderate events may cause some interference with functioning.
- **Severe** – Events interrupt a participant's usual daily activity and may require systemic drug therapy or other treatment. Severe events are usually potentially life-

threatening or incapacitating. Of note, the term “severe” does not necessarily equate to “serious”.

The degree of certainty about causality will be graded using the categories below.

- **Related** – The AE is known to occur with the study intervention, there is a reasonable possibility that the study intervention caused the AE, or there is a temporal relationship between the study intervention and event. Reasonable possibility means that there is evidence to suggest a causal relationship between the study intervention and the AE.
- **Not Related** – There is not a reasonable possibility that the administration of the study intervention caused the event, there is no temporal relationship between the study intervention and event onset, or an alternate etiology has been established.

Adverse events will also be classified as **expected** or **unexpected**. An AE will be considered unexpected if the nature, severity, or frequency of the event is not consistent with the risk information previously described for the study intervention. Based on the information contained in the package insert for Rabivax-S, the following adverse events are considered expected:

- Local reactions (limited to the site of the injection): pain, erythema, oedema, pruritus and induration.
- Systemic reactions: fever, shivering, malaise, asthenia, faintness, dizziness, headache, myalgia, arthralgia, nausea and abdominal pain.

- Hypersensitivity or allergic reactions: anaphylaxis, urticaria, rash and erythema multiforme.

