15.3 IDENTIFICATION OF ADVERSE EVENTS

The Study Coordinator will review the Visit 1-3 CRFs daily for participants receiving injections (dose 1, 2 or 3). The study coordinator will send a link to an online Qualtrics survey (Appendix H) by email on day 3 after the date of the injection (dose 1, 2 or 3) to all participants. Information on occurrence of expected AEs will be specifically solicited in the survey, by asking the question, “Since receiving the study injection 3 days ago, did you experience any of the following...?” and providing participants with a list of expected AEs (see **Section 15.2, Classification of adverse events** for details) from which to select. Participants will also be asked to grade the severity of any AEs (mild, moderate or severe) and the outcome (recovered/resolved without sequelae, recovered/resolved with sequelae or ongoing). Information on occurrence of other AEs (unsolicited) will be sought by asking the question, “Besides the signs listed above, have you noticed anything different since starting the study?”, and providing participants the opportunity to describe what they noticed or experienced, and grade the severity and outcome as above.

Participants will also be encouraged to report any adverse events to RUSVM Student Health Services (unsolicited adverse events). An adverse event form (Appendix I) will be completed for all adverse events reported to RUSVM Student Health Services, using the Vaccine Adverse Event Reporting System (VAERS) writable PDF form (https://vaers.hhs.gov/pdf/vaers_form.pdf). The Principal Investigator, together with the

Director of the RUSVM Student Health Services, will review and compare the reports of unsolicited adverse events (adverse event forms) against reports of solicited adverse events in the AE surveys, to avoid double capture.

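### Safety Endpoint 2 mixes the illnesses the vaccine is meant to prevent with events it might cause, and the two causality categories in Section 15.2 can both apply to one event

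*Combined protocol and SAP*

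**What the plan says.** Safety Endpoint 2 (Section 3.2.4) is the "Number of unsolicited adverse events and SAEs reported to RUSVM Student Health Services through four weeks after first injection", and the objective is to compare its rate between arms.

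Section 15.1 defines an adverse event to include any symptom or disease "temporally associated with the subject's participation in the research, whether or not considered related" to participation. It makes no exception for the study syndromes. Section 15.3 requires an adverse event form to be "completed for all adverse events reported to RUSVM Student Health Services".

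Secondary Endpoint 6 (Section 3.2.2) draws on the same clinic. It is "defined as an episode resulting in a visit to the RUSVM Student Health Services with a recorded ICD10" for acute nasopharyngitis, influenza, diarrhea or unspecified fever. Efficacy follow-up starts 10-14 days after allocation (Section 3.2.1).

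The only check for duplicates, in Section 15.3, compares adverse event forms with the solicited adverse event surveys. Section 14 describes the analysis of the primary and secondary endpoints, and the SAP it promises is to cover those endpoints. Neither is said to cover safety.

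On causality, Section 15.2 gives three alternatives that make an event *Related*, the last being "or there is a temporal relationship between the study intervention and event". It gives three that make an event *Not Related*, the last being "or an alternate etiology has been established". Section 15.4 sends nonserious events that are both unexpected and considered related to the IRB within 48 hours.

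**The concern.** The trial tests whether the vaccine lowers the rate of colds, influenza-like illness, diarrhea and fever. If the same illnesses also make up part of the unsolicited adverse event count, a real benefit lowers the vaccine arm's count and can balance events the vaccine causes. Even with no benefit, a large background of ordinary illness pulls the rate ratio towards 1. A neutral Safety Endpoint 2 would then be hard to interpret.

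The causality wording raises a second problem. A confirmed viral illness a week after an injection is *Related* by its timing and *Not Related* by its established cause, and the text gives no rule for choosing. Upper respiratory illness and diarrhea are not on the expected list, so the choice decides whether such an event goes to the IRB within 48 hours. It also decides the related-event counts. Only participants are blinded (Sections 4 and 11.3), and clinic staff hold the allocation (Section 11.2), so ambiguous grading could differ by arm.

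**Working it through.** **The plan's own figure.** Section 8 gives 215 per arm from a control rate of 2 episodes per 26 weeks, rate ratio 0.75, exposure fraction 0.8, dispersion 0.4, 80% power and "Alpha level = 0.05" (two-sided, Section 14). With the true-rates variance:

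n = (1.960 + 0.842)² × [(1/0.8)(1/2 + 1/1.5) + 2 × 0.4] / (ln 0.75)² = 214.2, rounded up to 215 per arm. The figure reproduces, so its inputs are used below.

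**Study-syndrome episodes in the four-week window.** This assumes a constant rate and no dropout in the first four weeks.

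- Control: 215 × 2 × 4/26 = 66.2
- Vaccine, protection from day 0: 66.2 × 0.75 = 49.6
- Difference: 16.5
- Difference if protection acts only on days 10-28 (18 of 182 days): 215 × 2 × 18/182 × 0.25 = 10.6

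**Share reaching the clinic.** The documents give no figure, so this is an assumption shown over a range. The offset is the difference multiplied by the share.

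| Share of episodes reported to the clinic | Offset, protection from day 0 | Offset, days 10-28 only |
|---|---|---|
| 10% | 1.7 | 1.1 |
| 20% | 3.3 | 2.1 |
| 30% | 5.0 | 3.2 |
| 50% | 8.3 | 5.3 |
| 100% | 16.5 | 10.6 |

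**Effect on the comparison.** The background rate and the harm are also assumptions. Suppose 5% of controls have another unsolicited event (215 × 0.05 = 10.75), the vaccine truly doubles this (21.5), and 20% of syndrome episodes reach the clinic (13.2 control, 9.9 vaccine with protection from day 0).

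- Other events alone: 21.5 / 10.75 = 2.00
- Total, no benefit: (21.5 + 13.2) / (10.75 + 13.2) = 1.45, which is pure dilution
- Total, with benefit: (21.5 + 9.9) / (10.75 + 13.2) = 1.31

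A Poisson approximation to the log rate ratio at two-sided 0.05 puts power at about 46% for the other events alone and about 17% for the total. The plan specifies no safety test, so these figures only show how much signal is lost.

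**When the harm cancels completely.** The clinic share needed is the excess harm divided by 16.5.

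- 5% background, true ratio 1.5: excess 5.4, share about 32%
- 2% background, true ratio 1.5: excess 2.15, share about 13%
- 10% background, true ratio 2.0: excess 21.5, share about 130%, so full cancellation cannot occur

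**Causality wording.** No arithmetic applies. The three conditions in each category are joined by *or*, so any one is enough. A confirmed infection soon after injection satisfies the last condition of each list.

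**The case against.** Several points on the other side stand.

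- The offset of 16.5 is a ceiling. It needs every mild illness to reach the clinic and full protection from day 0, before doses 2 and 3. The protocol itself treats latency as exploratory (Section 3.2.3).
- Much of the lost signal is dilution rather than hidden benefit.
- Overlap with efficacy follow-up starts only at about day 10-14. Earlier illnesses are adverse events only, and fever in the three days after an injection is solicited under Safety Endpoint 1.
- Event type remains visible on each form. Solicited reactions are collected after every dose, and serious events go to the IRB whatever their cause. Section 3.2.4 names a number of events; it does not say that only a pooled total will be shown.
- Section 12 describes separate routes for clinic episodes and adverse event forms, so a form for every clinic visit with a cold is not certain. Sections 15.1 and 15.3 read together do support it, and nothing excludes it.

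A reader might also infer that the temporal condition turns every syndrome episode in both arms into a 48-hour IRB report. The documents do not support that. Fever is on the expected list, so influenza-like and undifferentiated febrile illness are not plainly unexpected. Section 3.2.4 identifies the study intervention as the vaccine, so control-arm illnesses arguably fall outside the rule, although Section 6.2 uses the term more loosely. Section 15.2 also bases the assessment on clinical judgment as well as timing.

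A further tempting step would be to make the events outside the study syndromes the main safety comparison. Section 2.1 notes that non-live vaccines may have harmful non-specific effects, and the efficacy test is two-sided. Ranking the lines that way would demote a plausible harm, namely excess infection.

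**Conclusion.** The concern holds in a limited form. As written, Safety Endpoint 2 combines events of opposite expected direction, and no passage separates them. This dilutes a harm signal and can partly offset it. Full cancellation needs a small harm or high clinic attendance.

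The offset is about 1 to 8 events at an assumed 10-50% attendance, with a ceiling of about 16.5 (about 10.6 if protection begins at day 10). These figures rest on the Section 8 rates, a constant rate over time and an attendance share that the documents do not give.

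The overlap of the causality categories follows from the wording alone. It affects related-event counts and which unexpected events go to the IRB, but no number of reports can be supported from the text. Sample size and the primary analysis are unaffected.

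**What to change.** 1. In Section 3.2.4, and in the SAP, report Safety Endpoint 2 by arm on three lines: unsolicited adverse events that meet a study-syndrome definition or carry an Endpoint 6 code; all other unsolicited adverse events; and the total. Do not rank one line as the main comparison, so that an excess of infections stays as visible as any other harm.
2. State in Section 15.3 how a clinic visit for a study syndrome is handled as an adverse event.
3. Reword Section 15.2 so that the two categories are mutually exclusive. *Related* should require a reasonable possibility of causation, with timing as supporting evidence and not sufficient by itself. *Not Related* should apply when no such possibility exists, including when another cause is established.

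The cost is a wording change and one or two more table lines, from data already on the adverse event form and in the clinic record.

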3.2.5 VACCINE EFFICACY ANCILLARY STUDY

OBJECTIVES	ENDPOINTS	JUSTIFICATION FOR ENDPOINTS
Vaccine efficacy ancillary study		

 • To compare, between participants in each group over three consecutive cohorts (Spring 2019, Summer 2019 and Fall 2019)(n = ~350), concentrations of rabies virus neutralizing antibody (RVNA) before first injection (day -7) and six months after first injection (day 180). • As a secondary objective, sub-group analysis for potential effect measure modification of vaccine efficacy endpoint by sex (males or females) 	
 • Geometric mean concentration (GMC) of RVNA titers measured by rapid fluorescent foci inhibition test (RFFIT) on sera samples collected 7 days before injection (day -7) and 6 months after first injection (day 180). 	

3.2.6 IMMUNOLOGY ANCILLARY STUDY

OBJECTIVES	ENDPOINTS	JUSTIFICATION FOR ENDPOINTS
Immunology ancillary study		

 • To compare, between 20 consecutively enrolled participants in each group (n = 40), 
 1) cytokine response of isolated peripheral blood mononuclear cells (PBMCs) stimulated with antigens unrelated to rabies vaccine antigens 	
 1. Concentration of TNFα, IL-1β, IL-6, IFNγ and IL-17 by ELISA assays or Luminex system on day 0, 21 and 90 after first injection 2. Expression of 84 genes involved in innate and adaptive immune responses, using custom RT2 Profiler PCR arrays on day 0, 21 and 90 after first injection 	

OBJECTIVES	ENDPOINTS	JUSTIFICATION FOR ENDPOINTS

2) innate and adaptive immune gene expression profile of isolated PBMCs stimulated with antigens unrelated to rabies vaccine antigens
 
3) changes in the proportion of monocyte and lymphocyte subpopulations upon stimulation with antigens unrelated to rabies vaccine antigens
	
3. Proportion of monocyte and lymphocyte subpopulations of peripheral blood mononuclear cells analyzed in a flow cytometer on day 0, 21 and 90 after first injection
	

